In addition to their 3x weekly for 3 weeks PBM or Sham-PBM treatments, participants will report to the study team in person approximately 3 weeks (+/- 3 days) and 6 weeks (+/- 3 days) after the start of their PBM or Sham-PBM treatment to complete the follow-up questionnaires (Appendix E), turn in their Pain Diary (Appendix F), and undergo ultrasound imaging to measure changes in plantar fascia thickness at 3-weeks and 6-weeks (see below).

Long-term follow-up questionnaires may be captured remotely (e.g., entered directly into REDCap using a personalized coded link with no log-in required, verbally over the phone with a study team member, etc.), or in-person (using Appendix U Long-Term Follow-Up Data Collection CRF) at approximately 3 months (+/- 10 days) post-start of PBM treatment. For Sham-PBMT participants who cross-over, their 3-month follow-up will be timed from the first day of their active PBM treatment, not their Sham-PBM treatment. Reminder phone calls and emails will be sent to participants at the phone and email address provided to the study team before the 3-month follow-up time point.

Participants will be evaluated for adverse events at each follow-up time point and any complications will be documented.

Study participation ends after the 3-month follow-up research activities are completed. Participants initially randomized to the PBMT group will participate in the study for approximately 3 months. Participants initially assigned to the Sham-PBMT group who choose to crossover and receive active PBMT post-unblinding will be in the study for approximately 4.5 months total. If the participant is a biological female of child-bearing age and/or capacity, they will be required to complete another hCG urine pregnancy test at this time. Results must be negative (i.e., indicating not pregnant) to be eligible to continue with PBM treatment. If the results are positive (i.e., indicating pregnant), the participant will be deemed ineligible by formal screening criteria, and they will be ineligible to receive the elective study treatment.

Ultrasound Measurement:

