The local study team will collect study data directly from the study participant (including in person, via mail or email, or over the phone), from their attending provider(s), clinical evaluations or, where applicable, from the participant's medical record (i.e., relevant medical and treatment history and relevant clinical notes) and record it on study Case Report Forms (CRFs) (see Appendices A-F, T-U).

The completed CRFs will serve as source documents for this study. Other source documents include relevant clinical notes, imaging, and/or test results which, if applicable, will be redacted and stored in the participant's research file.

Participants may also enter their coded data directly into REDCap using a personalized survey link (no log-in required). In these cases, the completed REDCap questionnaire(s) will be printed and added to the participant's research record as a source document.

Electronic Data Entry:

Following each research visit, a local study team member will review any completed paper CRFs for accuracy and completeness and then enter the collected non-personally identifiable data from the paper CRFs into REDCap, an encrypted, access controlled, password protected electronic data capture and management system housed on a Department of Defense (DoD) server and maintained by the Uniformed Services University Information Technology (USU IT).

Please see Appendix R for additional information on REDCap.

Ultrasound images will be uploaded to Teleray, more information is outlined below.

Data Storage & Access:

With the exception of the Informed Consent Form, HIPAA Authorization, Intake CRF, and electronic Master List (see Appendix G), all research data (both paper and electronic) will be identified using a unique study ID only, and not by the participant's name, date of birth, DoD ID, or other protected identifier.

Paper research forms and source documents will be stored in a locked cabinet inside of a locked room within the Podiatry Clinic.

Ultrasound images will be uploaded to Teleray. Teleray ensures that all accounts stored in Microsoft Azure's self-healing network with advance security protocols enabled and is only located in the USA Secure Connection: The sessions established are secure (with secured tokens

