We are also requesting to store identifiable data for possible use in future research. Participants will be given the option to opt-in or opt-out for the possible use of their identifiable data in future research.

Data Withdrawal from Storage:

Participants may request to have their data withdrawn at any time before their personal identifiers have been removed. Once their data has been de-identified, it will be impossible for the researchers to locate their specific study data.

Is this a	data repository?	

If Yes, provide the name of the Repository

USU OCIO REDCap

Who will have access to the Repository?			
MIRROR core team members, study investigators and study team members, as appropriate			
What data type will be stored in the Repository?			
□ PHI			
LDS			
✓ De-identified Data			
11.0			
Statistical/Data Analysis Plan			
11.1 Statistical Considerations:			
List the statistical methods to be used to address the primary and secondary objectives, specific aims, and/or research hypotheses. Explain how missing data and outliers will be handled in the analysis. The analysis plan should be consistent with the study objectives. Include any subgroup analyses (e.g., gender or age group). Specify statistical methods and variables for each analysis. Describe how confounding variables will be controlled in the data analysis. Descriptive statistics for each variable will be reported as central tendencies in terms of location (e.g., mean, median) and scale (e.g., variance, interquartile interval). Inferential analyses will use the Mann-Whitney U test (a non-parametric analogue of Student's t-test) for simple comparisons and regression analysis with outcome-appropriate distribution families and link functions for multivariable comparisons. The FAAM sports subscale will be standardized by the multiplicative inverse of the patient-level maximum possible score. The primary outcome will be computed as the patient-level, six-week change in standardized FAAM sports subscale. Sensitivity analyses will be conducted using regression to control for patient-level demographics. Hypothesis tests will be two-tailed and statistical significance will be considered at the putative threshold (alpha=0.05). Effect sizes will be compared to a minimum clinically important difference.			
11.2 Sample Size:			
Assuming approximately 20% attrition, we are requesting to enroll up to 100 participants (approx. 50 per arm).			

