11.5 Please provide a justification for your sample size			
We found that enrolling 78 and retaining at least 60 patients by the six-week follow-up would be sufficient to yield >80% power for a moderate effect size (Mean six-week decrease in FAAM sports subscale: delta = 0.20) and a moderate standard deviation in effect (Std dev of six-week change in FAAM sports subscale: SD = 0.2), assuming the control effect mean and standard deviation are 0 and 0.22, respectively. Under similar constraints but with a standard deviation <0.18, the study would yield power >90%. Power was estimated using 1 million iterations of a Monte Carlo simulation based on effect means and standard deviations estimated from pilot data. Technical details will be made available upon request.			

In order to meet enrollment goals during the expected period of performance, recruitment will be expanded in addition to the current load of plantar fasciitis patients receiving care in the MAMC Orthopaedic and Podiatry clinics (a conservative estimate of approximately 80 patients per month), to reach potential participants receiving care in other departments including Family Medicine, Physical Therapy, and Physical Medicine & Rehabilitation (PM&R) clinics.	
11.6 Data Analysis Plan: Complete description: Background, Objectives, Design, Step by St project is going to be done, Data analysis plan:	ep how the
Descriptive statistics for each variable will be reported as central tendencies in terms of location (e.g., mean, median) and scale (e.g., variance, interquartile interval). Inferential analyses will use the Mann-Whitney U test (a non-parametric analogue of Student's t-test) for simple comparisons and regression analysis with outcome-appropriate distribution families and link functions for multivariable comparisons. The FAAM sports subscale will be standardized by the multiplicative inverse of the patient-level maximum possible score. The primary outcome will be computed as the patient-level, six-week change in standardized FAAM sports subscale. Sensitivity analyses will be conducted using regression to control for patient-level demographics. Hypothesis tests will be two-tailed and statistical significance will be considered at the putative threshold (alpha=0.05). Effect sizes will be compared to a minimum clinically important difference. Data will be analyzed on a complete-case basis with regards to each planned analysis. For	

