The potential participant will be given a copy of the informed consent document to read before, during, and/or after discussion of the informed consent with the Research Coordinator, Principal Investigator, Associate Investigator, or other authorized study team member. Sufficient time will be given to the potential participant to understand the study purpose, study procedures, time commitments, potential risks and benefits, and the types of health information that will be accessed, collected, and used by the research team if they agree to participate in the study. Questions can be raised by the potential participant at any time during the consent discussion

and also at any time during the conduct of the study. The potential participant will be instructed that their participation is completely voluntary and that they may withdraw from the study at any time without penalty. Their decision to participate or to not participate, or to withdraw from the study after consent, will not affect their access to health care that they are otherwise entitled to and it will not affect their military position.

The authorized study team member present during the consent conversation will confirm that the potential participant has no additional questions before deciding to provide consent.

Every effort will be made to eliminate the perception of authority, which is a particularly important consideration when recruiting active-duty study participants. When applicable, the study investigators will be in scrubs or civilian clothes instead of uniform and will introduce themselves as doctor rather than their military rank. Some potential participants may be patients of the study PI or AI. In these cases, the consent conversation will be initiated by non-physician study staff to prevent any misconception of coercion or undue influence.

Informed consent and HIPAA authorization will be obtained in person.

In the event that there are significant new findings regarding the therapy that may affect participants' willingness to continue in the study, an information sheet will be provided to all current and past participants. The informed consent document will be amended for future participants.

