Following completion of informed consent, the results of the Inclusion/Exclusion CRF will be entered into REDCap, an encrypted, access controlled, password protected electronic data capture and management system housed on a DoD server and maintained by the Uniformed Services University Information Technology (USU IT), and a unique study ID will be generated. This coded study ID will be used on all research data collection forms in place of the participant's name, Department of Defense (DoD) ID, or other protected identifier. No PII will be entered into REDCap. Please see Appendix R for additional information on REDCap.

13.5	DoDI 3216.02 requires an ombudsman to be present during recruitment briefings when research
	involves greater than minimal risk and recruitment of Service members occurs in a group setting. If
	applicable, you may nominate an individual to serve as the ombudsman.

N/A

Propose ombudsman

13.6 Withdrawal from Study Participation:

Explain the process for withdrawal and specify whether or not the subjects will be given the opportunity to withdraw their data their data/specimens in the event they wish to withdraw from the study

Participant Withdrawal:

Participants may withdraw from the study at any time without penalty. Participants will be informed that withdrawal will not affect their access to health care that they are otherwise entitled to and it will not affect their military position.

If a participant withdraws from the study, we may retain and analyze all coded/de-identified data collected up to the time of withdrawal if the data is necessary to maintain the integrity of the study. However, no further data will be collected after the date of withdrawal.

Participants may contact the study research coordinator/assistant or Principal Investigator to formally withdraw from the study. Participants will be advised to follow-up with their personal physician if they choose to withdraw.

Withdrawal Without Participant Consent:

A participant may be withdrawn from the study without their consent if remaining in the study might be dangerous or harmful to them. Participation may also be stopped if the military mission requires it, if they lose their right to receive medical care at a military hospital, if the study is canceled, if they fail to adhere to the protocol and/or therapy plan, or if they display inappropriate behavior towards study personnel.

The reason for any withdrawal/removal will be documented.

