15.0 Study Monitoring

♠ DSMP

15.1 Your study requires either Data and Safety Monitoring Plan (DSMP) or a Data and Safety Monitoring Board (DSMB).

O DSMB	
C Both	

Not Applicable

A DSMP should describe the plan to monitor the data to verify that the data are collected and analyzed as specified in the protocol. Include who will conduct the monitoring, what will be monitored, and the frequency of monitoring. It should also include the plan to ensure the safety of subjects

Participant Safety Monitoring Plan:

To ensure the safety of participants the PI will:

- Monitor the conduct of the protocol per the approved study plan and ensure protection of human participants. This may involve periodic review of medical records and/or research files of enrolled participants.
- 2. Review and keep abreast of adverse events and protocol deviations that occur during the research.
- 3. Review and sign adverse event logs/reports, protocol deviation logs/reports, and continuing reviews/annual progress reports.
- 4. If there is concern about the welfare of enrolled participants, the PI will stop the research study in progress, remove individual participants from a study, and take whatever steps necessary to protect the safety and well-being of research participants until the IRB can assess the situation.
- 5. Ensure that all study team members keep current required human subjects research trainings which require renewal every 3 years.

If an adverse event or protocol deviation occurs, it will be evaluated by the Principal Investigator and appropriate actions will be taken as outlined in Section 16.0 Reportable Events. In the case of an emergency, first responders will be called. In order to address the challenge of early identification of an increased risk of a known adverse event, all adverse event data will be tracked and evaluated.

On-site physicians will monitor the progress and health of the participants alongside our Principal Investigator. Participants can elect to withdraw from the study at any time. Participants may also be taken out of the study at any point if a research provider (or one of their treating providers) determines that it is no longer safe for them to continue with the study. If a participant elects to drop out of the study or is withdrawn for safety reasons, they will resume standard of care treatment with their assigned health provider(s).

Data Monitoring Plan:

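### Section 13.6 stops all data collection at voluntary withdrawal with no safety exception, so the later course of an adverse event still open at exit cannot be collected, even with the participant's agreement

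*Combined protocol and SAP*

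**What the plan says.** Section 13.6 treats two kinds of exit separately.

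- **Voluntary withdrawal.** Coded data collected up to that point may be retained and analysed if needed for the integrity of the study. Then: "However, no further data will be collected after the date of withdrawal". On care, the text says: "Participants will be advised to follow-up with their personal physician if they choose to withdraw".
- **Withdrawal without the participant's consent.** Grounds are listed, such as danger to the participant or non-adherence. The bar on further data is not repeated here.

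The reason for exit is documented in either case.

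On safety, section 10.1 states: "Participants will be evaluated for adverse events at each follow-up time point and any complications will be documented". Section 14.2 repeats the evaluation at follow-up visits and sends all adverse events to the principal investigator. Section 16.1 sets reporting routes and deadlines that run from discovery. Section 10.14 permits data to be taken by phone from the participant, and also "from their attending provider(s), clinical evaluations or, where applicable, from the participant's medical record".

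**The concern.** The named device risks in section 14.1 are eye damage and uncomfortable skin heating. For either one, whether it persisted or cleared is the main clinical fact. A person with such a reaction may well decide to leave. Under 13.6 as worded, staff who know of the reaction may not collect how it developed. That holds even if the participant would gladly take a call, and even if the personal physician they were advised to see has recorded the answer.

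What is at stake is the completeness of a few safety records. The study could report that a reaction occurred in someone who withdrew, but not how long it lasted or whether it resolved. The efficacy comparison is unaffected.

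**Working it through.** No calculation decides this point. The check is whether any section shown lifts the bar in 13.6, and then what the bar covers.

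**Does anything override it?**

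1. Section 10.1 (Follow-Up Data Collection) and section 14.2 tie adverse-event evaluation to follow-up time points. A participant who has withdrawn no longer attends these. No exception is given.
2. Section 10.14 opens the provider and medical-record routes in general terms. For a voluntary leaver, the specific sentence in 13.6 closes them.
3. Section 15.1 returns drop-outs to ordinary care under their own providers. That covers their treatment, but it does not tell the study the outcome.
4. Section 16.1 requires reports within set times of discovery. It creates no duty to follow an event to its end.
5. Section 18.4 makes the principal investigator responsible for reporting unanticipated adverse effects to the FDA. It does not address data collection after withdrawal.

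None of these overrides 13.6.

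**What does the bar cover?**

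- Event voiced before exit: recorded, retainable and reported to the investigator. Not lost.
- Later course of that event after voluntary withdrawal: collection barred.
- Treatment adjusted or ended for uncomfortable warmth (14.2): the text does not say participation ends, so such a person can apparently stay enrolled and be evaluated at later visits. Not barred.
- Removal without consent: no bar stated, and the routes in 10.14 stay open.

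**How many could be affected?** The documents give no count of voluntary withdrawals and no count of events open at exit. The only related figures are the planning allowances for attrition from all causes:

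- Section 11.2: "Assuming approximately 20% attrition, we are requesting to enroll up to 100 participants (approx. 50 per arm"), which gives 0.20 × 100 = 20 leavers.
- Section 11.5: "enrolling 78 and retaining at least 60 patients by the six-week follow-up", which gives 78 − 60 = 18, and 18 / 78 = 23%.

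These allowances include removals to which the bar does not apply and participants who could not be reached. They are not an estimate of the number affected. Only voluntary leavers with an event still open count, and the documents give no rate for that.

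**The case against.** The strongest reply is that 13.6 states an ordinary and respectful default: when a person leaves, collection stops. In a trial that recruits active-duty personnel and takes care in section 13.4 to remove any sense of authority, a bright line is defensible. This stands, and the fix keeps the default.

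A second reply also stands. Sections 15 and 16 as shown contain no follow-to-resolution rule for any participant. Deleting the sentence in 13.6 would therefore not by itself get outcomes recorded. The sentence forbids collection, but it is not the sole cause of a missing outcome.

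A reader might infer more than the documents support:

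- **That 13.6 contradicts section 15.1**, which says "all adverse event data will be tracked and evaluated". The full sentence there concerns early detection of an increased risk of a known event. Occurrence before exit is still recorded, so the two texts can stand together.
- **That no adverse-event check is made at exit.** The case report forms and the Adverse Event Tracking Log are not shown, so this cannot be concluded.
- **That the plan already accepts contact of this kind**, because section 13.4 says "an information sheet will be provided to all current and past participants". That is one-way information about new findings, and no precedent for collecting data after withdrawal.

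None of these replies supplies an exception for a leaver who agrees to be followed.

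**Conclusion.** The point holds as a minor one. For voluntary withdrawal only, the plan as written does not let the study collect the later course of an adverse event open at exit, even by agreement. The number of participants concerned cannot be estimated from the documents. It may be zero, and it is likely very small given the minimal-risk classification in section 16.1 and the description of the harms in section 14.1 as very rare.

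It would go too far to say that reactions in leavers go unrecorded, that leavers are left without care, or that the safety or efficacy conclusions are compromised. The documents support none of these.

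The conclusion rests on the text shown. The consent form was not available, and it may already contain terms for safety contact after withdrawal.

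**What to change.** In 13.6, keep the sentence "However, no further data will be collected after the date of withdrawal" and add to it: *except that, with the participant's agreement, any adverse event open at withdrawal will be followed by phone until it resolves or until the 3-month time point, whichever comes first.* Bring the consent form into line if it does not already say so.

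The cost is a wording amendment and a few phone calls by existing staff. Phone collection is already provided for in sections 10.1 and 10.14, and contact details are taken at intake. Participants who decline remain unfollowed, as now.

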14.0 Risks and Benefits

14.1

Risks of Harm:

Identify all research-related risks of harm to which the subject will be exposed for each research procedure or intervention as a result of participation in this study. Consider the risks of breach of confidentiality, psychological, legal, social, and economic risks as well as physical risks. Do not describe risks from standard care procedures; only describe risks from procedures done for research purposes

Research Procedure Name: Photobiomodulation (PBM) Therapy Research Procedure Description: Light therapy for Plantar Fasciitis (PF)

The potential risks directly associated with study-specific activities and procedures are minimal. PBM treatment is used by a variety of healthcare practitioners for painful clinical conditions. Potential research-related risks include damage to eye structures and uncomfortable skin heating, which are both very rare.

Additionally, any time information is collected for a study, there is a small risk of breach of confidentiality.

14.2

Measures to Minimize Risks of Harm (Precautions, safeguards):

For each research procedure or intervention, describe all measures to minimize and/or eliminate risk of harms to subjects and study personnel

Protective eyewear will be worn by all participants and study team members during treatment sessions to avoid damaging their eyes.

All applicable study team members will complete a battery of training modules and hands-on training sessions to ensure safe operation of the PBMT device, and compliance with local laser safety requirements and American National Standards Institute (ANSI) standards Z136.1 (Safe Use of Lasers) and Z136.3 (Safe Use Lasers in Health Care). See Appendix K for the laser operator training plan.

A member of the research team will serve as a clinical laser safety officer (CLSO) to establish and manage the study-specific laser safety program. The designee will work with the MAMC Laser Safety Officer (LSO) and participate in the MAMC Laser Safety Committee (LSC) meetings quarterly to receive proper training. Along with the LSO and CLSO, the PI will ensure that the treatment space meets all regulatory requirements for utilization of a treatment laser, including appropriate signage and use of laser blocking screens to absorb any potential scatter/refraction of light outside of the treatment area.

In the rare occurrence that participants experience uncomfortable warmth over the treatment area, the treatment will be modified or stopped.

In order to protect participant confidentiality, research data will be identified using a unique study ID only, and not by participant name, date of birth, DoD ID, or other similar identifier. All available measures allowed by law will be taken by research staff to protect participant confidentiality. See protocol section 14.3 for additional information

All participants will be evaluated for adverse events at each follow-up visit. All adverse events, regardless of severity, will be reported to the Principal Investigator. Adverse events will also be reported according to the guidelines stated in Protocol Section 16.

14.3 Confidentiality Protections (for research records, data and/or specimens):

Describe in detail the plan to maintain confidentiality of the research data, specimens, and records throughout the study and at its conclusion (e.g., destruction, long term storage, or banking). Explain the plan for securing the data (e.g., use of passwords, encryption, secure servers, firewalls, and other appropriate methods). If data will be shared electronically with other team members/collaborators outside the institution, describe the method of transmission and safeguards to maintain confidentiality. Explain whether this study may collect information that State or Federal law requires to be reported to other officials or ethically requires action, e. g., child or spouse abuse

Upon consenting for the study, participants will be assigned a unique study ID. With the exception of the Informed Consent Form, HIPAA Authorization, and electronic Master List, all research data (both paper and electronic) will be identified using this unique study ID only, and not by the participant's name, date of birth, DoD ID, or other protected identifier.

Paper research forms and source documents will be stored in a locked cabinet inside of a locked room within the Podiatry Clinic, accessible only by local research staff designated and authorized by the Principal Investigator. The paper Intake CRF which records participant contact information, Informed Consent Forms and HIPAA Authorizations will be stored separately from the coded paper research forms in a locked cabinet inside of a locked room within the Podiatry Clinic, accessible only by authorized local research staff.

The coded electronic research data for this study will be stored in REDCap, an encrypted, access controlled, password protected electronic data capture and management system housed on a Department of Defense (DoD) server and maintained by the Uniformed Services University Information Technology (USU IT). No PHI/PII will be entered into REDCap or Teleray. See Appendix R for additional information on REDCap.

The local study team will maintain a separate electronic Master List which matches the unique study IDs with participant identifying information. The electronic Master List will be stored separately from the coded electronic research data in a secure, password-protected electronic document on a computer and network that requires CAC access.

All research data and forms (both paper and electronic) will only be accessible by authorized study staff, the IRB of record, the local research office, and applicable governmental agencies as part of their duties and in accordance with federal law (except as stated in the next paragraph). These duties include making sure that research participants are protected.

Musculoskeletal Injury Rehabilitation Research for Operational Readiness (MIRROR), which is based out of the Department of Physical Medicine & Rehabilitation (PM&R) at the Uniformed Services University (USU), is serving as the data coordinating center for this research study. As such, authorized staff from MIRROR/USU will have access to the coded research data that is entered into REDCap. Authorized staff from MIRROR/USU will not have access to the electronic Master List, the paper research records, or any participant PHI/PII.

There will be appropriate data sharing agreements in place.

Any research data shared with an approved agency for review will be linked only to the participant's unique study ID and not with the personal identity of the participant (i.e., name, DOB, DoD ID, address, phone number, etc.). If the research data is used in scholarly presentations or journal articles, the investigators will protect the anonymity of individual participants and report only aggregate data (e.g., group means) where appropriate. Participants will not be individually identified in any publication or presentation of research results.

14.4

Potential Benefits:

Describe any real and potential benefits of the research to the subject and any potential benefits to a specific community or society

If the individuals in the research are considered experimental subjects (per 10 USC 980), and they cannot provide their own consent, the protocol must describe the intent to directly benefit all subjects

We cannot guarantee that participants will benefit from participation in this research study. However, participants could experience relief of heel/foot pain and improved function, which may be accelerated for those in the PBMT group.

Additionally, information learned from their participation in this study may help individuals with PF in the future.

14.5

Privacy for Subjects:

Describe the measures to protect subject's privacy during recruitment, the consent process, and all research activities, etc.

Recruitment, consent conversations, and follow-up research activities will take place in a private setting (e.g., closed clinic room, investigator's office, etc.) to minimize the potential opportunity to be overheard or inadvertently witnessed. Information being collected will be limited to only the minimum amount of data necessary to accomplish the proposed research.

14.6

Incidental or Unexpected Findings:

Describe the plan to address incidental findings and unexpected findings about individuals from screening to the end of the subject's participation in the research. In cases where the subject could possibly benefit medically or otherwise from the information, state whether or not the results of screening, research participation, research tests, etc., will be shared with subjects or their primary care provider. State whether the researcher is obligated or mandated to report results to appropriate military or civilian authorities and explain the potential impact on the subject

There is the possibility incidental findings could reveal information the participant would not otherwise be aware of. In cases where the participant could possibly benefit medically or otherwise, the participant will be notified and, when appropriate, so will their primary care provider. Research representatives will not share incidental and unexpected findings with anyone else unless required by law.

In cases involving military personnel, information regarding their health may be required to be reported to appropriate medical or command authorities to ensure the proper execution of the military mission, including evaluation of fitness for duty.

Although unlikely, incidental findings could impact a participant's future ability to receive health or life insurance, as is the case with all medical care. Incidental findings may also make the participant feel anxious.

